6. The comparisons between groups on the C-peptide and glucose in terms of basal to 180 min time course will be carried-out using a mixed linear model with C-peptide and glucose derived from the MMTT as dependent variables, treatment group, visit, time, treatment by visit interaction, time by visit interaction and treatment by time by visit interaction as fixed factors of the model and patient as random effect. An unstructured covariance matrix for each patient is considered and the Kenward-Roger adjustment is used for the degrees of freedom. Furthermore, default summary statistics of Cmax and Tmax of the MMTT at each visit will be provided. Cmax and Tmax will be calculated up to 180 minutes after mixed meal administration (time interval ranging from 15 min. to 180 min.). Individual plots will be presented. Based on the observed trends, additional analyses might be performed.
7. Number and proportion along the 95% confidence interval (Clopper-Pearson's formula) of patients maintaining a residual  $\beta$ -cell function at the single time points will be calculated. The comparison between the two study treatment arms will be performed by means of a Chi-square test or, if more appropriate, a Fisher's Exact test at each time point.
8. Number and proportion along the 95% confidence interval (Clopper-Pearson's formula) of patients with HbA1c < 7% and absence of episodes of severe hypoglycemia from the previous visit will be calculated for each time point. The comparison between the two study treatment arms will be performed by means of a Chi-square test or, if more appropriate, a Fisher's Exact test at each time point.
9. The comparisons between groups on C-peptide AUC (15-120) above fasting value will be carried-out using a mixed linear model where the  $\log(x+1)$  transformed C-peptide AUC above fasting value will be the dependent variable, while treatment group, visit, treatment by visit interaction will be the fixed factors of the model and patient will be the random effect. An unstructured covariance matrix for each patient is considered and the Kenward-Roger adjustment is used for the degrees of freedom.

---

Document: MEX0114\_SAP\_v4\_4 Final Methods.docx  
Author: [name]

Version Number:  
Version Date:

Final Version 4.4  
[17SEP2019]

Template No: CS\_TP\_BS016 – Revision 4  
Effective Date: 01Apr2016

Reference: CS\_WI\_BS005

## 16.3. EXPLORATORY AND POST-HOC ANALYSES

### 16.3.1. EXPLORATORY VARIABLES

The exploratory variables are:

1. Basal (2 basal samples in the range between -20 to 0 min) to 180 min time course of glucagon derived from the MMTT [Time frame: baseline, weeks 13±1, 26±2 and 52±2].
2. Auto-antibodies (GAD, IA-2, IAA, ZnT8), [Time frame: baseline, weeks 13±1, 26±2 and 52±2].
3. MicroRNA-375 expression level (miR-375) [Time frame: baseline, weeks 13±1, 26±2 and 52±2].
4. T-cell response ex vivo to major  $\beta$ -cell antigens (e.g. pro-insulin, GAD65) - selected sites only [Time frame: baseline, weeks 13±1, 26±2 and 52±2].
5. 2-hour AUC of C-peptide response to the MMTT stratified by the number of positivity in auto-antibodies (1, 2, 3, and 4) at Screening visit.
6. Proportion of responders at week 52, defined as patients with percent decrease from baseline in 2-hour AUC of C-peptide above the median percent decrease from baseline to Week 52.

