## 3. STUDY OBJECTIVES AND ENDPOINTS

### 3.1. STUDY OBJECTIVES

The objective of this clinical trial is to investigate whether Ladarixin has sufficient activity (preservation of  $\beta$ -cell function and slowdown of the progression of type 1 diabetes) to warrant its further development. The safety of Ladarixin in the specific clinical setting will be also evaluated.

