## 5.3. FINAL ANALYSIS

All final, planned analyses identified in this SAP will be performed by SPARC Consulting, Milan, Italy on behalf of IQVIA RDS Italy, Milan, Italy following Sponsor Authorization of this Statistical Analysis Plan, Database Lock, Sponsor Authorization of Analysis Sets and Unblinding of Study Treatment.

The default summary statistics for quantitative variables will be the number of observations (n), mean, standard deviation (SD), median, minimum (min) and maximum (max) for those patients with data. For quantitative efficacy variables, standard error of the mean (SEM) and lower and upper 95% confidence limits (CI) for mean will be also presented.

For qualitative variables, the number (n) and percentage (%) of patients with non-missing data per category will be the default summary presentation, and where appropriate and present, the number of missing values as a "Missing" category. If appropriate, 95% confidence intervals around the proportions will be presented using the Clopper-Pearson's formula.

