## 7.5. STATISTICAL TESTS

All statistical tests will be performed one sided with  $\alpha=0.05$  and 95% confidence intervals will be employed, unless otherwise specified in the description of the analyses.

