## 7.6. COMMON CALCULATIONS

For some quantitative measurements, change from baseline will be calculated as:

- Absolute: Value at Visit X – Baseline Value

---

Document: MEX0114\_SAP\_v4\_4 Final Methods.docx  
Author: [name]

Version Number:  
Version Date:

Final Version 4.4  
[17SEP2019]

Template No: CS\_TP\_BS016 – Revision 4  
Effective Date: 01Apr2016

Reference: CS\_WI\_BS005

- Relative:  $((\text{Value at Visit X} - \text{Baseline Value}) / \text{Baseline Value}) * 100$

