### 8.3. MISSING DATA

If the actual time for Mixed Meal Tolerance Test is not recorded, the scheduled time will be used.

Missing C-peptide values will be imputed with the average of the C-peptide value that precedes and follows the missing value. Missing data in C-peptide at 180 minutes (final) will be replaced by the last non-missing value.

The last available basal sample time will be used as the first sample time in the computation of the AUC, and the average of the basal sample values (Basal #1 and Basal #2) will be used as the first sample value in the computation of the AUC.

Other missing data will not be replaced.

The number of patients with missing data will be presented under the “*unknown*” category. Missing values will be included in the denominator count when computing percentages.

When continuous data will be summarized, only the non-missing values will be evaluated for computing summary statistics.

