## 16.2. SECONDARY EFFICACY ANALYSES

### 16.2.1. SECONDARY EFFICACY VARIABLES

The secondary efficacy variables are:

1. 2-hour AUC of C-peptide response to the MMTT [Time points: baseline, weeks 13±1, 26±2 and 52±2].
2. Percent change from baseline of 2-hour AUC of C-peptide response to the MMTT [Time points: weeks 13±1, 26±2 and 52±2].
3. Average (previous 3 days) insulin requirement (IU/kg/day) [Time points: baseline, weeks 13±1, 26±2 and 52±2].  
For the patients reporting “off insulin” response in the CRF the daily insulin requirement value will be conventionally set to zero in the statistical analysis.
4. HbA1c levels [Time points: baseline, weeks 13±1, 26±2 and 52±2].
5. Number of severe hypoglycemic events occurring from randomization [Time points: weeks 13±1, 26±2 and 52±2].  
A severe hypoglycemic event is defined as an event with one of the following symptoms: “Memory loss, confusion, uncontrollable behavior, irrational behavior, unusual difficulty in awakening, suspected seizure, seizure, loss of consciousness, or visual symptoms”, in which the patient was unable to treat him/herself and which was associated with either a blood glucose level < 54 mg/dL or prompt recovery after oral carbohydrate, i.v. glucose, or glucagon administration.
6. Basal (2 basal samples in the range between -20 to 0 min) to 180 min time course of C-peptide and glucose derived from the MMTT [Time points: baseline, weeks 13±1, 26±2 and 52±2].
7. Proportion of patients maintaining a residual β-cell function [Time points: baseline, weeks 13±1, 26±2 and 52±2].  
Maintenance of a residual β-cell function is defined as at least one MMTT C-peptide value > 0.2 nmol/L.
8. Proportion of patients with HbA1c < 7% and absence of episodes of severe hypoglycemia from the previous visit [Time points: weeks 13±1, 26±2 and 52±2].
9. C-peptide AUC (15-120 minutes) above fasting value [Time points: baseline, weeks 13±1, 26±2 and 52±2].

Document: MEX0114\_SAP\_v4\_4 Final Methods.docx  
 Author: [name]

Version Number:  
 Version Date:

Final Version 4.4  
 [17SEP2019]

Template No: CS\_TP\_BS016 – Revision 4  
 Effective Date: 01Apr2016

Reference: CS\_WI\_BS005

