### 16.3.2. ANALYSIS OF EXPLORATORY VARIABLES

Data will be summarized for all patients in the ITT population, by treatment group.

For the endpoint #1, the comparisons between groups on glucagon in terms of basal to 180 min time course will be carried-out using a mixed linear model with glucagon derived from the MMTT as dependent variables, treatment group, visit, time, treatment by visit interaction, time by visit interaction and treatment by time by visit interaction as fixed factors of the model and patient as random effect. An unstructured covariance matrix for each patient is considered and the Kenward-Roger adjustment is used for the degrees of freedom. Furthermore, default summary statistics of Cmax and Tmax of the MMTT at each visit will be provided. Cmax and Tmax will be calculated up to 180 minutes after mixed meal administration (time interval ranging from 15 min. to 180 min.).

For the endpoints from #2 to #4 default summary statistics of the values over time and the changes from baseline will be provided.

For the endpoint #5, the comparisons between groups will be carried-out using a mixed linear model with 2-hour AUC of C-peptide response to the MMTT as dependent variable, treatment group, visit, number of positivity in auto-antibodies at Screening visit, treatment by visit interaction, treatment by number of positivity interaction as fixed factors of the model and patient as random effect. An unstructured covariance matrix for each patient is considered and the Kenward-Roger adjustment is used for the degrees of freedom.

Analysis of endpoint #6 will be performed calculating the number and proportion along the 95% confidence interval (Clopper-Pearson's formula) of patients responder. The comparison between the two study treatment arms will be performed by means of a Chi-square test or, if more appropriate, a Fisher's Exact test.

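### The week-52 responder definition, read as written, counts the patients who lost more C-peptide as responders

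*SAP*

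**What the plan says.** - **Definition.** SAP 16.3.1 item 6 defines responders at week 52 as "patients with percent decrease from baseline in 2-hour AUC of C-peptide above the median percent decrease from baseline to Week 52". SAP 4.3 item 6 uses the same words.
- **Analysis.** SAP 16.3.2: "Analysis of endpoint #6 will be performed calculating the number and proportion along the 95% confidence interval (Clopper-Pearson's formula) of patients responder", with a chi-square test or, if more appropriate, Fisher's exact test between arms. It gives no sign convention and does not say whether the median is pooled or taken per arm.
- **Objective.** SAP 3.1 asks whether the drug has enough activity (preservation of beta-cell "function and slowdown of the progression of type 1 diabetes) to warrant its further development".
- **Relative change.** SAP 7.6 opens with "For some quantitative measurements, change from baseline will be calculated as" and gives (visit value − baseline) / baseline × 100, so a loss is negative. It names no endpoint.
- **Neighbouring endpoint.** SAP 16.2.1 item 2, on the same variable, is worded "Percent change from baseline of 2-hour AUC of C-peptide response to the MMTT": change, not decrease.
- **Sidedness.** SAP 7.5: "All statistical tests will be performed one sided with" alpha 0.05, unless otherwise specified. SAP 16.3.2 does not specify otherwise.
- **Denominator.** SAP 5.3: "the number (n) and percentage (%) of patients with non-missing data per category will be the default summary presentation". SAP 8.3: "Missing values will be included in the denominator count when computing percentages".

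**The concern.** In ordinary English, a decrease above the median decrease is a bigger fall. A programmer who follows the sentence will flag the half of patients who lost the most C-peptide and call them responders. An effective drug would then be expected to show fewer responders than placebo. A one-sided test for a higher responder rate on ladarixin would almost never succeed, and a small two-sided p-value could be reported beside proportions that point the wrong way.

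The sentence can also be read in the other direction by treating the decrease as the signed change of SAP 7.6. Two competent programmers could therefore produce opposite endpoints from the same text.

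**Working it through.** The documents give no figure for this endpoint, so there is none to reproduce. The check applies both readings to the same data.

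**1. Direction.** Let C = (week 52 − baseline) / baseline × 100, as in SAP 7.6, and let D = −C be the percent decrease.
- Literal: responder if D > median(D).
- Signed: responder if C > median(C).

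Take six made-up patients with C = +5, −10, −20, −40, −60, −80. The median of C is −30 and the median of D is 30. The literal responders are −40, −60 and −80; the signed responders are +5, −10 and −20. The two sets are exact complements.

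**2. Numbers evaluable.** SAP 4.1.2 gives 72 patients and 24% drop-out; SAP 4.1.3 gives 2:1 allocation. 72 × 0.76 = 54.7, so 54 or 55 evaluable; 54 splits as 36:18. A pooled-median split of 54 gives 27 responders.

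**3. Fixed tables at 36:18.** The signed count is the arm size minus the literal count.

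| Literal (ladarixin vs placebo) | Signed | Two-sided Fisher, both readings | Chi-square (uncorrected), both readings | One-sided Fisher, literal | One-sided Fisher, signed |
|---|---|---|---|---|---|
| 15/36 vs 12/18 | 21/36 vs 6/18 | 0.148 | 0.083 | 0.979 | 0.074 |
| 14/36 vs 13/18 | 22/36 vs 5/18 | 0.042 | 0.021 | 0.996 | 0.021 |
| 13/36 vs 14/18 | 23/36 vs 4/18 | 0.0084 | 0.0039 | 0.9994 | 0.0042 |

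One-sided means ladarixin greater. The undirected p-values are the same under both readings; the one-sided p-value moves from one tail to the other.

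**4. Odd count.** With 55 evaluable, the patient at the median is a responder under neither reading, so the sets are not complements. Literal 13/37 vs 14/18 gives two-sided p = 0.0041. Signed gives 0.0090 if the median patient is on ladarixin (23/37 vs 4/18) or 0.0013 if on placebo (24/37 vs 3/18).

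**5. Expected size.** These inputs are assumptions, not document figures: retained AUC fraction lognormal, placebo median 0.6 or 0.7, log-SD 0.35 or 0.5, pooled median, 10,000 simulated trials per setting. At 36:18, with ladarixin retaining 1.3 to 1.5 times the placebo fraction:
- Literal rates are 36-43% on ladarixin against 64-79% on placebo; signed rates are 57-64% against 21-36%.
- Two-sided Fisher p < 0.05 with fewer literal responders on ladarixin occurs in 27-86% of trials.
- One-sided Fisher in favour of ladarixin is significant in at most 0.05% of trials (literal) against 27-86% (signed).
- With no drug effect, both arms sit at about 49-50% under either reading.
- At a ratio of only 1.1, literal rates are about 46-47% against 55-57%, and a significant reversal occurs in about 7-10% of trials.

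**6. Pooling.** If medians were taken per arm, each arm would show about 50% by construction and the comparison would be empty.

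**7. Denominator.** Suppose there is no drug effect and, by assumption, 40/48 and 14/24 patients are evaluable. Responders are then 20 and 7: 50% vs 50% of non-missing patients, but 20/48 = 41.7% vs 7/24 = 29.2% of all patients.

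**The case against.** The best defence is that the direction is implied. The patients are called responders, the objective is preservation, the only relative-change formula in the SAP is signed, and that variable is already derived for SAP 16.2.1 item 2, which does not cite SAP 7.6 either. ADaM specifications and table shells, named in SAP 5 but not available here, may settle the sign; SAP 5 also requires double programming and review by the lead biostatistician. This makes the signed reading the likely intent. It does not make it the text: SAP 7.6 covers unnamed measurements and defines change, while this rule says decrease. Double programming does not help if both programmers follow the same sentence.

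A second objection is that chi-square, not Fisher, is the first-choice test. Expected counts at 36:18 are 18, 18, 9 and 9, and the ordinary 2×2 chi-square has no direction. That stands: the reversed one-sided test arises only with Fisher or a signed statistic. Chi-square would still not reveal the reversal, and at 36:18 it crosses 0.05 at the same table as two-sided Fisher (14/36 vs 13/18).

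Third, the error would be visible. Proportions and intervals are printed by arm, and the week-52 AUC and percent-change models (SAP 16.2.2 items 1 and 2) would point the other way. That also stands and limits the harm.

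Fourth, the denominator is a separate matter of missing detail, and the unequal drop-out used to illustrate it has no support in the documents. That is fair, and the conclusion does not rest on it.

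**Conclusion.** The concern holds. As written, in both places, the rule selects the larger losses, and nothing in the SAP fixes the sign the other way. The direction of the error needs no assumption; its size does. The 27-86% chance of a significant reversed result depends on the assumed ratios of 1.3 to 1.5, a pooled median and 36:18 evaluable. It falls to about 7-10% at a ratio of 1.1, and SAP 4.1.2 offers no variability figures from which to choose. With an odd number evaluable, the 0.05 verdict differs between the two definitions in 4-17% of trials at ratios 1.3 to 1.5 (4-8% at 37:18, 8-17% at 36:19).

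This should be fixed, but it does not threaten the trial's conclusion: the endpoint is exploratory and SAP 8.4 treats only the primary comparison as confirmatory. That the signed formula was meant is an inference, though a strong one.

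**What to change.** Before treatment codes are opened, replace the definition in SAP 4.3 item 6 and SAP 16.3.1 item 6 with:

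> Patients whose percent change from baseline to Week 52 in 2-hour AUC of C-peptide (signed, formula of section 7.6) is greater than the median of both treatment groups pooled, i.e. a percent decrease below the pooled median decrease. The median is taken over ITT patients with both a baseline and a Week 52 AUC.

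In SAP 16.3.2, add one sentence saying which of SAP 5.3 or SAP 8.3 governs the denominator for this endpoint, and use that denominator both for the reported percentages and for the chi-square or Fisher table. Check the ADaM specification and table shell against the new wording.

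The cost is one sentence in two places and one in SAP 16.3.2, with no new data. Timing matters because a direction or denominator chosen after unblinding would be a data-driven choice.

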#### 4.1.2. SAMPLE SIZE

Seventy-two (72) patients with new-onset T1D will be randomized, after consenting in written for the study and after having undergone clinical investigations for compliance with the selection criteria and approval by the Investigator.

According to the  $\log(x+1)$  transformed data [initially selected by TrialNet as the appropriate transformation for MMTT C-peptide AUC] and the sample size calculated on the data stratified by an adult population (> 18 years), 72 patients will provide 85% power to detect a 50% between-group difference in the 2-hour MMTT C-peptide AUC (2:1) at 0.05 significance level (one-sided test), assuming a 24% drop-out rate.

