#### 4.1.3. DESCRIPTION OF TREATMENTS

Patients will be randomized with a 2:1 ratio to either Ladarixin or placebo. The Investigational Medicinal Product

Document: MEX0114\_SAP\_v4\_4 Final Methods.docx  
 Author: [name]

Version Number: Final Version 4.4  
 Version Date: [17SEP2019]

Template No: CS\_TP\_BS016 – Revision 4  
 Effective Date: 01Apr2016

Reference: CS\_WI\_BS005

(IMP) will be provided as hard gelatin capsules for oral administration. Ladarixin will be administered orally at the dose of 400 mg twice a day for 3 cycles of 14 days on / 14 days off. Placebo will be administered with the same treatment schedule.

The two daily doses will be administered at about 12 hours' interval (morning and evening; ideally between 8.30/9.30 and 20.30/21.30). At each administration, 2 capsules will be swallowed with a glass of water, at least 2 hours apart from breakfast or dinner.

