- 3) The analysis corresponding to the average insulin requirement secondary efficacy endpoint has been reformulated as “The comparisons between groups on insulin requirement secondary efficacy endpoints will be carried-out using a mixed linear model with average daily insulin requirement as dependent variable, treatment group, visit, treatment by visit interaction as fixed factors of the model and patient as random effect. An unstructured covariance matrix for each patient is considered and the Kenward-Roger adjustment is used for the degrees of freedom.” In the study protocol, the following was stated: “The mean in average daily insulin requirement at the 4 time points (baseline, weeks 13±1, 26±2 and 52±2) will be analysed using a repeated measurements model using PROC MIXED within SAS®.”
- 4) The analysis corresponding to the HbA1c secondary efficacy endpoint has been reformulated as “The comparisons between groups on HbA1c secondary efficacy endpoint will be carried-out using a mixed linear model with HbA1c value as dependent variable, while treatment group, visit, treatment by visit interaction as fixed factors of the model and patient as random effect. An unstructured covariance matrix for each patient is considered and the Kenward-Roger adjustment is used for the degrees of freedom.” In the study protocol, the following was stated: “The mean in HbA1c value at the 4 time points (baseline, weeks 13±1, 26±2 and 52±2) will be analysed using a repeated measurements model using PROC MIXED within SAS®.”
- 5) In the study protocol, the default summary statistics for quantitative variables were the number of observations (n), mean, standard deviation (SD), standard error of the mean, median, minimum (min) and maximum (max), lower and upper 95% confidence limits for those patients with data.

This was modified as follows:

“The default summary statistics for quantitative variables will be the number of observations (n), mean, standard deviation (SD), median, minimum (min) and maximum (max) for those patients with data. For quantitative efficacy

Document: MEX0114\_SAP\_v4\_4 Final Methods.docx

Author: [name]

Version Number:

Final Version 4.4

Version Date:

[17SEP2019]

Template No: CS\_TP\_BS016 – Revision 4

Reference: CS\_WI\_BS005

Effective Date: 01Apr2016

variables, standard error of the mean and lower and upper 95% confidence limits (CI) will be also presented.”

- 6) The analyses of new efficacy endpoints have been planned:

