  - Proportion of patients maintaining a residual  $\beta$ -cell function [Time points: weeks 13 $\pm$ 1, 26 $\pm$ 2 and 52 $\pm$ 2].
  - C-peptide AUC (15-120 min) above fasting value [Time points: baseline, weeks 13 $\pm$ 1, 26 $\pm$ 2 and 52 $\pm$ 2].
  - Percent change from baseline of 2-hour AUC of C-peptide response to the MMTT [Time points: weeks 13 $\pm$ 1, 26 $\pm$ 2 and 52 $\pm$ 2].
  - Proportion of patients with HbA1c < 7% and absence of episodes of severe hypoglycemia from the previous visit [Time points: weeks 13 $\pm$ 1, 26 $\pm$ 2 and 52 $\pm$ 2].
  - Proportion of responders at week 52, defined as patients with percent decrease from baseline in 2-hour AUC of C-peptide above the median percent decrease from baseline to Week 52.
- 7) Planned subgroups descriptive analyses on the efficacy endpoints according to age class at Screening ( $\leq$  25 and > 25 years) and to fasting C-peptide (Pre-MMTT) ( $\leq$  median value and > median value) at Screening visit.
- 8) A subgroup analysis on 2-hour AUC of C-peptide response to the MMTT stratified by the number of positivity in auto-antibodies (1, 2, 3, and 4) at Screening visit has been planned.
- 9) The approach to deal missing C-peptide values has been changed: the sentence “missing C-peptide values will be imputed via linear interpolation” of the study protocol has been changed in “Missing C-peptide values will be imputed with the average of the C-peptide value that precedes and follows the missing value. Missing data in C-peptide at 180 minutes (final) will be replaced by the last non-missing value.”.
- 10) In the study protocol was stated “When C-peptide values are below the limit of detection (0.2 ng/mL), a value of 0.2 ng/mL will be assumed in the calculation of area under the curve.” This rule to address the C-peptide values below 0.2 ng/mL will not be applied. C-peptide values will analysed as reported in the CRF.

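### The week-52 responder cut is an unspecified median of the trial's own data, so the responder rate has no absolute meaning and its Clopper-Pearson intervals are miscalibrated (exploratory endpoint, minor)

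*SAP*

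**What the plan says.** SAP 16.3.1 item 6 counts as responders the "patients with percent decrease from baseline in 2-hour AUC of C-peptide above the median percent decrease from baseline to Week 52". SAP 4.3 item 6 repeats the definition in a list introduced by "The analyses of new efficacy endpoints have been planned". Neither place gives a number, an external source for the median, or the group it is taken over (all patients, placebo patients, or each arm separately).

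SAP 16.3.2 plans to analyse the endpoint by "calculating the number and proportion along the 95% confidence interval (Clopper-Pearson's formula) of patients responder". It adds: "The comparison between the two study treatment arms will be performed by means of a Chi-square test or, if more appropriate, a Fisher's Exact test".

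SAP 8.3 keeps missing values in the denominator of percentages. SAP 8.4 makes only the primary comparison confirmatory. The SAP's other two binary efficacy endpoints (16.2.1 items 7 and 8) use fixed cuts: a stimulated C-peptide above 0.2 nmol/L, and HbA1c below 7% without severe hypoglycaemia.

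**The concern.** A responder rate is normally read as an absolute success rate: the share of patients who reached a stated level. A cut taken from the sample's own median cannot supply that. If every patient lost most of their C-peptide, a pooled median would still label about half of them responders. The rate therefore says nothing about preservation of beta-cell function, which is the objective in SAP 3.1, and cannot be set beside a rate from another trial.

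The second issue is the interval. Clopper-Pearson treats each patient as an independent yes/no against a fixed threshold. With a pooled median the total number of responders is fixed, which ties the two arm counts together. With a placebo-arm median the threshold carries the sampling error of a small arm. Binomial variance is wrong in both cases, in opposite directions, and the SAP does not say which case applies.

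**Working it through.** **Inputs.** "Seventy-two (72) patients with new-onset T1D will be randomized" (SAP 4.1.2) and "Patients will be randomized with a 2:1 ratio to either Ladarixin or placebo" (SAP 4.1.3), hence 48 v 24. SAP 4.1.2 assumes 24% drop-out: 72 x 0.76 = 54.7. Taking 54 evaluable gives 36 v 18 if drop-out is proportional, and 54/0.76 = 71.05 rounds up to the planned 72. The documents state no figure for the responder endpoint, so there is none to reproduce. The direction of the inequality does not affect this arithmetic.

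**1. Totals and ceiling, pooled median, no ties.** Responders K = N/2.
- 48 v 24: K = 36, so 48 x p(ladarixin) + 24 x p(placebo) = 36. The ladarixin rate lies between (36 - 24)/48 = 25% and 36/48 = 75%. With normal data and an assumed 3 SD effect, its expected value is still only 74.5%.
- 36 v 18: K = 27, ceiling 27/36 = 75%.
- 54 evaluable, split unevenly (K = 27):

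| Evaluable, ladarixin : placebo | Ladarixin ceiling |
|---|---|
| 48 : 6 | 27/48 = 56% |
| 40 : 14 | 27/40 = 67.5% |
| 34 : 20 | 27/34 = 79% |
| 30 : 24 | 27/30 = 90% |

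The first and last rows put all drop-out in one arm.
- If the SAP 8.3 denominator rule applies here, 36 v 18 evaluable gives 27/72 = 37.5% responders overall and a ladarixin ceiling of 27/48 = 56%.

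**2. Spread of the ladarixin rate, 48 v 24, no effect.**
- Binomial (what Clopper-Pearson assumes): variance of the count 48 x 0.25 = 12, SD 3.46, or 7.2 percentage points.
- Pooled median: the count is hypergeometric, variance 48 x 0.25 x 24/71 = 4.06, SD 2.01, or 4.2 points. For placebo, 2.01/24 = 8.4 points against 10.2 binomial.
- Placebo-arm median: the true proportion lying above the median of 24 placebo values has variance of about 0.25/26 = 0.0096. The rate then has variance of about (0.25 - 0.0096)/48 + 0.0096 = 0.0146, SD about 12 points.

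**3. Coverage of the nominal 95% ladarixin interval, same setting.** Clopper-Pearson at n = 48 contains 50% when the count is 17 to 31, that is within 7 of 24.
- Pooled: 7.5/2.01 = 3.7 SDs. Exact hypergeometric coverage is about 99.99%; for placebo it is just over 99%.
- Placebo-arm: 7.5/48 = 15.6 points, and 15.6/12 = 1.3 SDs, giving about 80%. Simulation with normal data agrees, and gives 81% at 36 v 18.
- Fixed cut, for comparison: simulated coverage 97.1% (ladarixin) and 97.7% (placebo), the usual mild conservatism.

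The pooled interval can also include unattainable values. An observed 36/48 gives 60.4% to 86.4%, although 75% is the ceiling.

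**4. The between-arm test, pooled median, no effect.** Let d be the ladarixin count minus its expectation.
- 48 v 24: uncorrected chi-square is d² x (2/24 + 2/12) = d²/4. At d = 4 this is 4.0, above 3.84, so it rejects when |d| is 4 or more: 7.9% exactly. Two-sided Fisher needs |d| of 5 or more: 2.3%.
- 36 v 18: chi-square is d²/3. Both tests reject at |d| of 4 or more: 4.2%.

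**5. Within-arm median.** Both rates would be about 50% by definition and the comparison would be empty.

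**The case against.** The strongest reply is that the SAP never says the median is pooled. A reader might infer that half of all patients are responders and that ladarixin can never exceed 75%. The documents do not support this as a flat statement. With a placebo-arm median, placebo is fixed near 50% and ladarixin can reach 100%. Even with a pooled median, both figures depend on which patients are evaluable at week 52 and on the SAP 8.3 denominator rule. The table shells might settle the reference group, but they are not in the documents. This stands, which is why the finding is an unspecified data-derived cut and not a fixed 75% ceiling.

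A reader might also infer that the intervals could support a false claim of efficacy. On the pooled reading they are too wide, which is the safe direction. Under-coverage arises only if the median is the placebo arm's. Nor is the comparison invalid: with both margins fixed, Fisher's exact test is a proper median test. The planned choice between chi-square and Fisher is not equally safe, because uncorrected chi-square exceeds 5% at 48 v 24.

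Finally, the objective is addressed elsewhere. SAP 16.2 already has a fixed-cut beta-cell endpoint and a baseline-adjusted mixed model for percent change in AUC through week 52. The endpoint is listed as exploratory in 16.3.1, and its place among the new efficacy endpoints in 4.3 does not alter that. This limits the severity but does not repair the intervals.

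**Conclusion.** The point holds. The cut comes from the trial's own week-52 data and its reference group is not named. On the pooled reading the proportion carries no absolute meaning, and on either the pooled or the placebo-arm reading the ladarixin Clopper-Pearson interval is miscalibrated: SD 4.2 v 7.2 points and coverage about 99.99% (pooled), or SD about 12 v 7.2 points and coverage about 80% (placebo-arm).

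These figures assume 48 v 24 evaluable, no treatment effect and no ties; the placebo-arm coverage also uses normal data. The 75% ceiling requires a pooled median and exactly 2:1 evaluable data; with about 54 evaluable patients it ranges from 56% to 90%. Nothing here affects the primary analysis. Severity is minor.

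**What to change.** In SAP 4.3 item 6, 16.3.1 item 6 and 16.3.2:
- State that the median is the pooled median of patients evaluable at week 52, and call the analysis a median test.
- Name Fisher's exact test in place of the choice between chi-square and Fisher.
- Delete the per-arm Clopper-Pearson intervals for this endpoint, and report the between-arm difference in median percent change with its 95% interval, naming the method.

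This costs a few words and needs no new data. The same edit should settle which side of the median counts as response, since a decrease above the median is, read literally, the larger loss.

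Alternatively, before unblinding, replace the median by a fixed cut, chosen by the sponsor, on the percent change defined in SAP 7.6. Each rate is then a true binomial proportion and Clopper-Pearson is appropriate. The cost is that a value must be justified, and a poorly chosen one could give rates near 0% or 100%.
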